- 9 White blood cell count must be $< 10 \times 10^9/L$ prior to the first dose in Cycle 1, Day 1. Treatment with hydroxyurea (AML) or high-dose steroids (ALL and leukaemia of ambiguous lineage) during screening and Cycle 1 to control white blood cell count is permitted. Both medications can be started or stopped at any point during this period.
- 10 Adequate organ function at screening defined in [Table 3](#):

Table 3 Organ Function Parameters

Category	Parameter	Value
Hepatic	Total bilirubin	$\leq 1.5 \times \text{ULN}$
		$\leq 3 \times \text{ULN}$ in presence of Gilbert's syndrome
	AST and ALT	$\leq 2.5 \times \text{ULN}$
Coagulation	INR	$< 1.5 \times \text{ULN}$
Pancreatic	Lipase	$\leq 1.5 \times \text{ULN}$
	Amylase	$\leq 1.5 \times \text{ULN}$ and absence of clinical pancreatitis
Renal*	Serum creatinine	$\leq 1.5 \times \text{ULN}$
	CrCl by Cockcroft and Gault method: $\text{CrCl (mL/min)} = \frac{(140 - \text{age [years]}) \times \text{weight (kg)} \times (F)}{(72 \times \text{serum creatinine mg/dL})}$ ^a where F = 0.85 for females and F = 1 for males	$\geq 50 \text{ mL/min}$

*For patients with below ideal body weight, the 24-hour urine test may be used: ideal body weight (kg) = constant + 0.91 (height [cm] - 152.4); constant is 50 for men and 45.5 for women.

ALT, alanine transaminase; AST, aspartate transaminase; CrCl, creatinine clearance; INR, international normalised ratio; ULN, upper limit normal.

- 11 Adequate cardiac function as demonstrated by left ventricular ejection fraction (LVEF) $> 50\%$ on screening cardiac multigated acquisition (MUGA), magnetic resonance imaging (MRI), or echocardiogram (ECHO).

- 12 Willing and able to participate in all required study evaluations and procedures including receiving IV administration of study treatment and admission to the hospital, when required, for administration of study treatment and monitoring.
- 13 All patients must consent to and undergo both pretreatment and on-treatment fresh bone marrow aspirates and biopsies
- 14 For inclusion in the genetic component of the study, patients must fulfil the following additional criteria:
 - Provision of signed, written, and dated informed consent for genetic research. If a patient declines to participate in the genetic component of the study, there will be no penalty or loss of benefit to the patient. The patient will not be excluded from other aspects of the study described in this protocol, as long as they consented to the main study.

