Appendix F Management of Specific Adverse Events

F 1 Guidance for Management of Tumour Lysis Syndrome

Patients will be evaluated for clinical signs and symptoms of TLS during treatment with AZD0466, and blood samples will be collected according to the individual module SoA.

Recommendations for prophylaxis, management, dose modification, and adverse event reporting pertaining to TLS are summarised below.

F 1.1 Prophylaxis for TLS

Assessment of TLS risk is based on disease type, as summarised in [Table 31](#).

Table 31 Risk Assessment for Tumour Lysis Syndrome

Malignancy	Risk of tumour lysis syndrome ^a		
	High	Intermediate	Low
Acute myeloid leukaemia	WBC $\geq 100 \times 10^9/L$	WBC ≥ 25 and $\leq 100 \times 10^9/L$ or WBC $< 25 \times 10^9/L$ and LDH $\geq 2x$ ULN	WBC $< 25 \times 10^9/L$ and LDH $< 2x$ ULN
Acute lymphoblastic leukaemia	WBC $\geq 100 \times 10^9/L$ and LDH $\geq 2x$ ULN	WBC $< 100 \times 10^9/L$ and LDH $< 2x$ ULN	-

^a WBC $< 10 \times 10^9/L$ is required for study eligibility and hydroxyurea (AML) and high-dose steroids (ALL and leukaemia of ambiguous lineage) are permitted during screening and Cycle 1 to achieve this; consequently patients will be intermediate or low risk of TLS.

Risk classification adapted from MD Anderson Cancer Center guidance.

LDH, lactate dehydrogenase; TLS, tumour lysis syndrome; ULN, upper limit of normal range; WBC, white blood cell count.

Prophylaxis for TLS (hydration and anti-hyperuricaemic agents) is required for all patients receiving study treatment and should be implemented according to the TLS risk level assessed for each patient ([Table 31](#)). Specific recommendations are outlined in this section, but details of management may vary per institutional practice. Patients with creatinine clearance < 80 mL/min, and patients with renal involvement from underlying disease and/or urinary outflow obstruction, may be at higher risk of TLS and complications of TLS, and should be managed accordingly. Hospitalisation may be considered for hydration management requirements occurring outside of the protocol-scheduled inpatient hospitalisation period.

Prophylaxis is summarised by TLS risk score in [Table 32](#), according to the following principles:

- **Adequate oral fluid intake** ([Table 32](#)) is required for all patients receiving study treatment, in particular around the times of AZD0466 dosing, and patients should be

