encouraged to drink sufficient fluid (total of 1.5 to 2 L/day) before and after each infusion of AZD0466.

- **IV hydration** is required for all patients during the ramp-up in Cycle 1 (total > 2 L/day of IV and oral hydration). From Cycle 1 Day 15 onwards, IV hydration should be administered based on risk of TLS. Infusion of sodium chloride 0.9% IV (fluid composition may change based on patient need and Investigator discretion) should commence 2 to 4 hours before each infusion of AZD0466. At least 1 L of IV hydration should be administered over a 24-hour period. Additional IV hydration may be administered as clinically indicated in patients with diarrhoea and/or nausea and vomiting. Diuretics should be used with care and prophylactic use of diuretics should be used only if patients have signs of volume overload.
- **Allopurinol** (or other xanthine oxidase inhibitor) should be administered to all patients receiving study treatment and it is recommended to initiate it one calendar day before the first dose of AZD0466. 100 to 300 mg every 8 hours is suggested, but allopurinol dose may require adjustment as described in the allopurinol prescribing information or institutional guidelines.
- **Rasburicase** should be considered as an alternative to allopurinol for patients with elevated uric acid at baseline, or high tumour burden. Rasburicase should be administered 4 hours prior to AZD0466 infusion, and as described in the rasburicase prescribing information. It is recommended that investigators check for Glucose-6-Phosphate-Dehydrogenase (G6PD) as Rasburicase is contraindicated in patients with G6PD deficiency.

Table 32 Recommended Prophylaxis for Tumour Lysis Syndrome

	Risk of tumour lysis syndrome		
	High	Intermediate	Low
Recommended prophylaxis			
Hydration	Increased hydration: oral 1.5 to 2 L/day and IV 150 to 200 mL/h Maintain urine output	IV hydration required during ramp-up (total IV and oral fluids > 2 L/day) From Cycle 1 Day 15: oral hydration 1.5 to 2 L/day; consider IV hydration based on risk of TLS	
Anti-hyperuricaemics	Allopurinol 100 to 300 mg every 8 hours Early consideration of rasburicase ^a as an alternative, based on baseline uric acid and tumour burden		Allopurinol 100 to 300 mg every 8 hours
Criteria for use of rasburicase			
Serum uric acid at baseline	> 475.8 µmol/L ^b + 1 risk factor ≤ 475.8 µmol/L ^b + 2 risk factors	> 475.8 µmol/L ^b + 2 risk factors ≤ 475.8 µmol/L ^b + 3 risk factors	-

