Risk factors	Serum creatinine > 1.3 mg/dL (> 88.4 µmol/L) WBC > 50 ×10 ⁹ /L LDH > 2x ULN		-

^a Rasburicase is contraindicated in patients with glucose-6 phosphate dehydrogenase deficiency, known hypersensitivity to rasburicase, haemolytic anaemia or methemoglobinemia

^b Uric acid cut-off may be adjusted according to local guidance.

Recommended prophylaxis adapted from [University of Texas MD Anderson Cancer Center 2018](#), [Cairo and Bishop 2004](#), [Cairo and Bishop 2004](#)

, and [Howard et al 2011](#).

IV, intravenous; LDH, lactate dehydrogenase; ULN, upper limit of normal range; TLS, tumour lysis syndrome; WBC, white blood cell count.

F 1.2 AZD0466 Dose Modifications for TLS

AZD0466 dose modifications for TLS are summarised in [Table 33](#).

Table 33 AZD0466 Dose Modifications for TLS

Abnormality	Action with AZD0466
Laboratory findings (serum)	
Uric acid \geq 475.8 μ mol/L	
 Initiate supportive therapy as per standard clinical practice, additional guidance provided in Table 34.
Potassium \geq 6.0 mmol/L	
 Delay AZD0466 for up to 7 days (if finding present before administration of AZD0466)
Phosphate \geq 1.6 mmol/L (5.0 mg/dL) with \geq 0.16 mmol/L (0.5 mg/dL) increase*	
 If resolution to within specified threshold in \leq 7 days, restart AZD0466 at the same dose level
Corrected calcium $<$ 1.75 mmol/L	
 If resolution after 7 days, restart AZD0466 at one lower dose than the current dose.
Creatinine increase by $>$ 26.5 μ mol/L from baseline (creatinine $>$ 1.5 x ULN if no baseline)	
All laboratory abnormalities must resolve to within specified threshold before AZD0466 is restarted, with the exception of an isolated phosphate abnormality, in which instance restarting the dose may be discussed with the Medical Monitor.	
Clinical findings	
Signs suggestive of clinical TLS (eg, acute kidney injury, cardiac arrhythmia/dysrhythmia ^a , hypotension ^b , heart failure ^b)	
 Initiate supportive therapy as per standard clinical practice Delay AZD0466 for up to 14 days (if finding present before administration of AZD0466) Restart AZD0466 at one lower dose than the current dose following resolution

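### Table 32 prints two different creatinine cut-offs for the rasburicase risk factor: 1.3 mg/dL is 114.9 µmol/L, not 88.4 µmol/L

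*Protocol*

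**What the plan says.** Protocol Section 6.5.1 asks sites to consider rasburicase on the basis of Appendix F and institutional guidelines. In Appendix F 1.1, Table 32 sets the criterion by TLS risk group, baseline uric acid and a count of risk factors. The three factors are creatinine, WBC > 50 × 10⁹/L and LDH > 2 × ULN. The creatinine factor reads "Serum creatinine > 1.3 mg/dL", and a second figure follows in brackets as the equivalent, so that the pair is printed as "1.3 mg/dL (> 88.4" µmol/L.

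At intermediate risk, two factors are needed when uric acid is above 475.8 µmol/L and three when it is not. The low-risk column has no rasburicase criterion.

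Two other provisions decide whom this reaches:

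- Core inclusion criterion 9 (Section 5.1) requires WBC below 10 × 10⁹/L "prior to the first dose in Cycle 1, Day 1". The footnote to Table 31 concludes that "consequently patients will be intermediate or low risk of TLS".
- In Table 31, an AML patient with a WBC this low is intermediate risk only through the cell "WBC $< 25 \times 10^9/L$ and LDH $\geq 2x$ ULN". The intermediate cell for ALL requires LDH < 2 × ULN.

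**The concern.** A dual-unit threshold should define one rule. Here each unit defines a different one. Neither is named as governing, and the only table footnote that permits local adjustment concerns the uric acid cut-off. In a multi-centre study, sites reporting in mg/dL and sites reporting in µmol/L would classify the same patient differently.

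What is at stake is a prompt for prophylaxis. One reading could miss a patient who was meant to meet the criterion. The other could extend use of a drug that the protocol notes is contraindicated in G6PD deficiency. TLS is an adverse event of special interest (Section 8.3.12). Section 11.4.7.2 counts certain TLS as dose-limiting only when it occurs despite the management the protocol recommends, so that management should read the same at every site.

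**Working it through.** **Inputs.** The printed cut-offs, 1.3 mg/dL and 88.4 µmol/L, come from Table 32. The molar mass of creatinine, 113.12 g/mol, is a physical constant that the documents do not give.

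**Conversion.** µmol/L = mg/dL × 10,000 / molar mass, so the factor is 10,000 / 113.12 = 88.40 µmol/L per mg/dL.

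- 1.3 mg/dL → 1.3 × 88.4 = 114.9 µmol/L. The printed 88.4 is not reproduced.
- 88.4 µmol/L → 88.4 / 88.4 = 1.0 mg/dL.
- Difference: 114.9 − 88.4 = 26.5 µmol/L. Ratio: 114.9 / 88.4 = 1.30.

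**Control on neighbouring pairs.** In Table 35, uric acid 8.0 mg/dL converts to 475.9 µmol/L (printed 475.8), phosphate 4.5 mg/dL to 1.45 mmol/L (printed 1.5) and calcium 7.0 mg/dL to 1.75 mmol/L (printed 1.75). In Table 33, phosphate 5.0 mg/dL converts to 1.61 mmol/L (printed 1.6). These agree to rounding; the creatinine pair does not.

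**Who is affected.** At baseline the WBC > 50 factor is always 0, because entry WBC is below 10.

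| Patient (entry WBC < 10) | Factors without creatinine | Factors needed | Does creatinine decide? |
|---|---|---|---|
| AML, LDH > 2 × ULN, uric acid > 475.8 | 1 | 2 | Yes |
| AML, LDH > 2 × ULN, uric acid ≤ 475.8 | 1 | 3 | No, maximum is 2 |
| ALL in the printed intermediate cell (LDH < 2 × ULN) | 0 | 2 or 3 | No, maximum is 1 |
| Low-risk AML | – | no criterion | No |

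For the first row, at three creatinine values:

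- 80 µmol/L: not met under either cut-off.
- 100 µmol/L (1.13 mg/dL): met under 88.4 µmol/L, not met under 1.3 mg/dL.
- 120 µmol/L: met under both.

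An AML patient at exactly 2 × ULN is intermediate in Table 31 (≥) but lacks the LDH factor in Table 32 (>), so nothing changes for that patient.

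**Can an eligible patient lie in the band?** Table 3 requires Cockcroft-Gault clearance of at least 50 mL/min. For an assumed 60-year-old, 70-kg man:

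- at 1.0 mg/dL: (140 − 60) × 70 / (72 × 1.0) = 77.8 mL/min;
- at 1.3 mg/dL: (140 − 60) × 70 / (72 × 1.3) = 59.8 mL/min.

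Both pass. Table 3 also limits creatinine to 1.5 × ULN. For an assumed ULN of 0.9 to 1.3 mg/dL that limit is 119 to 172 µmol/L, above the whole band.

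**The case against.** The arithmetic is not in dispute; the strongest objection is that the error has little effect.

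- **Rasburicase is already prompted.** The affected patients are hyperuricaemic and at intermediate risk by construction. The text above Table 32 says rasburicase "should be considered as an alternative to allopurinol for patients with elevated uric acid at baseline", and the anti-hyperuricaemics row of the table asks for its early consideration, neither with a creatinine condition.
- **Local practice is allowed.** Appendix F 1.1 states that "details of management may vary per institutional practice", and Section 6.5.1 names institutional guidelines.
- **Reduced clearance is flagged separately.** Appendix F 1.1 singles out patients with clearance below 80 mL/min for management as possibly higher risk. The example patient is below 80 at both ends of the band.
- **The intended figure is unknown.** The table is adapted from guidance that the documents do not reproduce.

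The first two points stand and limit the practical effect, but neither says which creatinine figure to use.

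The third stands in part. A 60-year-old man reaches 80 mL/min at 80 × 72 × 1.0 / 80 = 72 kg when creatinine is 1.0 mg/dL, and at 80 × 72 × 1.3 / 80 = 93.6 kg when it is 1.3 mg/dL; heavier men of that age are not covered by the clause. If a site took the clause to mean the high-risk column, the ambiguity would move, not vanish. That column needs one factor above 475.8 µmol/L and two at or below it. Creatinine would then decide for hyperuricaemic patients without raised LDH, and for patients with LDH > 2 × ULN and uric acid at or below 475.8 µmol/L.

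The fourth is fair, and the fix leaves the choice to the clinical team.

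The limit to AML is also slightly too narrow. ALL with WBC < 100 × 10⁹/L and LDH ≥ 2 × ULN has no cell in Table 31. If such patients were handled as intermediate risk, those with LDH above 2 × ULN would be affected in the same way.

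**Conclusion.** The concern holds. Table 32 contains two creatinine thresholds, 1.0 and 1.3 mg/dL, presented as one. The risk-factor flag differs for any patient above 88.4 and up to 114.9 µmol/L. On the printed risk groups, the rasburicase criterion differs essentially only for intermediate-risk AML with LDH > 2 × ULN, baseline uric acid > 475.8 µmol/L and creatinine in that band. How many patients that is cannot be worked out from the documents.

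The eligibility check rests on an assumed patient and an assumed range for the ULN; the conversion rests on neither. The effect stops at an advisory prophylaxis criterion. No endpoint, eligibility rule, dose modification, sample size or analysis uses the figure. SAP Section 4.14.11 lists rasburicase prophylaxis for patients with TLS but does not apply the creatinine cut-off. The link to the TLS dose-limiting toxicity wording is indirect, and no toxicity call has been shown to change.

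The SAP records that recruitment stopped in June 2023, so a correction now serves the protocol of record and any reuse of this appendix.

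**What to change.** State one threshold in both units in Table 32. Either print > 1.3 mg/dL (> 115 µmol/L), or print > 1.0 mg/dL (> 88.4 µmol/L) if the clinical team wants the lower cut-off. The first is the likelier intention, because 88.4 is the bare mg/dL-to-µmol/L conversion factor, which suggests a multiplication left undone. That is an inference and should be confirmed against the source guidance.

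The cost is one number in one table, with no change to design, data collection or analysis.

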6.6.5 Cardiac findings

AZD0466 should be withheld if any of the following occur at any time during study treatment:

- Symptomatic tachycardia
- Symptomatic hypotension
- QTcF shortening by 60 milliseconds compared to baseline, or interval value < 340 milliseconds, confirmed on at least 2 separate ECGs recorded 5 minutes apart
- QTcF prolongation of > 500 milliseconds or QTcF prolongation from baseline by 60 milliseconds, confirmed on at least 2 separate ECGs recorded 5 minutes apart
- Any other cardiac findings of CTCAE Grade ≥ 2 if considered by the Investigator to be clinically significant

AZD0466 should be permanently discontinued if a CTCAE \geq Grade 3 cardiac AE of any duration occurs during study treatment, if considered by the Investigator to be related to study treatment.

Patients should be monitored closely including continuous ECG monitoring as clinically indicated (including for QTcF prolongations > 500 milliseconds) and until such a time as deemed safe to discontinue monitoring by medical review, with cardiologist input considered in the instance of abnormal ECG findings. AZD0466 may be restarted after resolution of

cardiac findings to the patient's baseline at the discretion of the Investigator and after discussion with the Medical Monitor.

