11.4.7.2 Dose-limiting Toxicity

Any event that meets the DLT criteria in the opinion of the Investigator should be reported to the Medical Monitor within 24 hours of knowledge of the event. Events will be assessed for DLT criteria according to the CTCAE National Cancer Institute (NCI) v5.0 (Section [8.3.2](#)) except for TLS, which will be assessed for DLT criteria using the Howard modification of Cairo-Bishop criteria ([Appendix G](#)). Toxicity that is clearly and directly related to the underlying malignancy or to an extraneous cause is excluded from the definition of a DLT. A DLT will be defined as the occurrence of any of the following:

- Any CTCAE Grade 3 non-haematological toxicity lasting > 7 days OR any CTCAE Grade 4 non-haematological toxicity, with the exception of:
 - CTCAE Grade 4 nausea, vomiting, or diarrhoea lasting < 7 days in the absence of maximum supportive therapy,
 - Elevation in serum amylase and/or lipase without clinical or radiographic evidence of pancreatitis,
 - CTCAE Grade 3 fatigue, asthenia, fever, anorexia, or constipation.
- Any other cardiac findings of CTCAE Grade ≥ 2 if considered by the Investigator to be clinically significant.
- AZD0466 should be permanently discontinued if a CTCAE Grade ≥ 3 cardiac AE of any duration occurs at any time during study treatment, if considered by the Investigator to be related to study treatment.
- AZD0466 should be permanently discontinued if liver function test abnormalities meets Hy's Law (HL) or Potential Hy's Law (PHL) criteria, and considered by the Investigator to be related to study treatment (see [Appendix E](#)).
- Prolonged myelosuppression: as myelosuppression and cytopenias are expected outcomes of leukaemia treatment, only the criteria defined below will be a DLT:
 - Lack of haematological recovery (ANC remaining $<0.5 \times 10^9/L$, platelets remaining $< 50 \times 10^9/L$) in the absence of active leukaemia in bone marrow (blasts $< 5\%$) and with marrow hypocellularity at $< 5\%$ by Day 42.
- Cairo-Bishop Grade ≥ 3 Clinical TLS ([Appendix G](#)) that occurs despite protocol-recommended management.
- Cairo-Bishop Laboratory TLS ([Appendix G](#)) with metabolic abnormalities that do not resolve within 5 days despite protocol-recommended management.
- Any other toxicity that
 - is greater than at baseline, is clinically significant and/or unacceptable, and is judged to be a DLT by the SRC, or
 - results in a disruption of dosing schedule of more than 21 days.

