Symptoms suggestive of clinical TLS ^a (eg, oliguria ^c , seizure, nausea, vomiting, muscle cramps ^b , neuromuscular instability ^b)	
 For clinical TLS, initiate supportive therapy and withhold AZD0466 until resolution of symptoms. AZD0466 can be withheld up to 14 days. Restart AZD0466 at one lower dose than the current dose level Patients should be encouraged to maintain oral hydration

^a Probably or definitely caused by hyperkalaemia or hypocalcaemia

^b Probably or definitely caused by hypocalcaemia

^c Average urine output of $<$ 0.5 mL/kg/h, lasting for $>$ 6 hours.

TLS, tumour lysis syndrome; ULN, upper limit of normal range.

*Recommended prophylaxis adapted from [University of Texas MD Anderson Cancer Center 2018](#), [Cairo and Bishop 2004](#), [Coiffier et al 2008](#), and [Howard et al 2011](#).

F 1.3 Treatment of TLS

Signs and symptoms of clinical TLS (including but not limited to acute kidney injury, oliguria, nausea, vomiting, seizure, muscle cramps, neuromuscular irritability, cardiac arrhythmia/dysrhythmia, hypotension, or heart failure) should be managed according to standard clinical practice. Additional IV hydration may be administered as clinically indicated in patients with diarrhoea and/or nausea and vomiting.

Recommendations for management of specific laboratory abnormalities is summarised in [Table 34](#).

Table 34 Recommended Management of Electrolyte Abnormalities in TLS

Abnormality	Management recommendations
Hyperphosphataemia	
Moderate (≥ 2.1 mmol/L)	Avoid IV and oral phosphate and limit dietary sources Administer phosphate binder
Severe	Dialysis or haemofiltration may be required
Hypocalcaemia (≤ 1.75 mmol/L)	
Asymptomatic	No therapy Patients with acute hypocalcaemia and hyperphosphataemia should not receive calcium repletion until phosphate level has normalised
Symptomatic	Calcium gluconate ^a 50 to 100 mg/kg by slow IV infusion with ECG monitoring
Calcium-phosphate product	
≥ 50 mg ² /dL ²	Ensure hydration is maintained and alkalinisation is discontinued
Hyperkalaemia	
Moderate (≥ 6.0 to < 7.0 mmol/L) and asymptomatic	Avoid IV and oral potassium ECG monitoring Administer sodium polystyrene sulfonate

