Appendix G Classification of Tumour Lysis Syndrome

G 1 Classification

The criteria for classification of laboratory and clinical TLS in adults are described below. These criteria are based on the [Howard et al 2011](#) modification of [Cairo and Bishop 2004](#), and have been adapted from [Cheson et al 2017](#).

Clinical TLS assumes the laboratory evidence of metabolic changes and an adverse event that requires clinical intervention. Clinical TLS is defined as the presence of laboratory TLS and any one or more of the clinical criteria, as specified in [Table 35](#) below.

Table 35 Criteria for Laboratory and Clinical Tumour Lysis Syndrome

Abnormality	Criteria
Laboratory TLS	
Two or more of the following metabolic abnormalities occurring during the same 24-hour period, and within 3 days before until 7 days after infusion of study treatment:	
Hyperuricaemia	Uric acid $\geq 475.8 \mu\text{mol/L}$ ($\geq 8.0 \text{ mg/dL}$)
Hyperkalaemia	Potassium $\geq 6.0 \text{ mmol/L}$
Hyperphosphataemia	Phosphate $\geq 1.5 \text{ mmol/L}$ ($\geq 4.5 \text{ mg/dL}$)
Hypocalcaemia	Corrected calcium $< 1.75 \text{ mmol/L}$ ($< 7.0 \text{ mg/dL}$), or Ionised calcium $< 0.3 \text{ mmol/L}$
Clinical TLS	
Laboratory TLS plus one or more of the following:	
Acute kidney injury	Serum creatinine increase by $> 26.5 \mu\text{mol/L}$ (or a single value $> 1.5 \times \text{ULN}$ if no baseline measurement), or oliguria (average urine output of $< 0.5 \text{ mL/kg/h}$) lasting for $> 6 \text{ hours}$
Cardiac arrhythmia/dysrhythmia or sudden death	Probably or definitely caused by hyperkalaemia or hypocalcaemia
Seizure	Probably or definitely caused by hypocalcaemia
Neuromuscular irritability, hypotension, or heart failure	Probably or definitely caused by hypocalcaemia

TLS, tumour lysis syndrome; ULN, upper limit of normal.

G 2 Grading

TLS should be graded according to the Cairo-Bishop criteria for the purposes of dose-limiting toxicity assessment ([Cairo and Bishop 2004](#)). The grade of the maximal clinical manifestation defines the overall grade of TLS, as summarised below in [Table 36](#).

Table 36 Grading of Tumour Lysis Syndrome

Cairo-Bishop Grading for TLS						
Abnormality	Grade 0	Grade 1	Grade 2	Grade 3	Grade 4	Grade 5
Laboratory TLS	Absent	Present	Present	Present	Present	Present
Serum creatinine ^a	< 1.5 x ULN	1.5 x ULN	> 1.5 – 3.0 x ULN	> 3.0 – 6.0 x ULN	> 6.0 x ULN	Death ^b

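### Table 33 allows a one-dose-lower restart after electrolyte-driven arrhythmia or heart failure without excepting the related Grade 3 or higher cardiac AEs for which Section 6.6.5 requires permanent discontinuation

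*Protocol*

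**What the plan says.** Protocol Appendix F 1.2, Table 33, has a row for clinical findings that begins "Signs suggestive of clinical TLS (eg, acute kidney injury, cardiac arrhythmia/dysrhythmia" and goes on to hypotension and heart failure. Footnote a limits the arrhythmia to one that is "Probably or definitely caused by hyperkalaemia or hypocalcaemia"; footnote b limits heart failure and hypotension to a hypocalcaemic cause. The actions are supportive care, a delay of up to 14 days if the finding is present before dosing, and then "Restart AZD0466 at one lower dose than the current dose following resolution". The restart bullet has no CTCAE or Cairo-Bishop grade limit, no permanent-stop branch and no cross-reference.

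Section 6.6.5 of the core protocol permanently stops AZD0466 for a CTCAE Grade 3 or higher "cardiac AE of any duration occurs during study treatment, if considered by the Investigator to be related to study treatment". Section 11.4.7.2 repeats this for Module 1, for a Grade 3 or higher "cardiac AE of any duration occurs at any time during study treatment, if considered by the Investigator to be related to study treatment". Neither exempts events caused by electrolyte disturbance.

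Appendix G 1 sets the definitions. Laboratory TLS needs "Two or more of the following metabolic abnormalities occurring during the same 24-hour period", from a list of four. "Clinical TLS is defined as the presence of laboratory TLS and any one or more of the clinical criteria".

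**The concern.** A related Grade 3 or higher arrhythmia or heart failure with an electrolyte cause can meet both rules. Table 33 then points to a restart at one lower dose, while Sections 6.6.5 and 11.4.7.2 point to a permanent stop. A site managing suspected TLS would naturally turn to the TLS dose-modification table, and nothing in that table tells it that the cardiac stop rule exists. At stake is whether a patient with a severe, drug-related cardiac event is re-exposed, and whether two sites would handle the same event alike. No endpoint or planned analysis is affected.

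**Working it through.** The plan gives no figure to reproduce and the documents give no event rate, so the check is a comparison of the rules.

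1. **Trigger.** The Table 33 row applies to signs *suggestive of* clinical TLS, which is wider than clinical TLS as defined in Appendix G. Its footnotes restrict cause only.

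2. **Stop rule.** It is stated in 2 sections (6.6.5 and 11.4.7.2). Table 33 cross-refers to 0 of the 2.

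3. **Does the TLS exception in 11.4.7.2 remove the clash?** That section grades events by CTCAE "except for TLS, which will be assessed for DLT criteria using the Howard modification of Cairo-Bishop criteria". This governs how TLS is judged as a DLT. It does not touch the discontinuation sentence.

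4. **Does the restart sentence in 6.6.5 remove it?** Section 6.6.5 also lets treatment resume once cardiac findings return to baseline, at the Investigator's discretion and after discussion with the Medical Monitor. That fits the findings for which the section says to withhold. It cannot sensibly undo a permanent stop.

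5. **An event inside Table 33 but outside clinical TLS.** Table 35 lists 4 metabolic abnormalities: uric acid, potassium, phosphate and calcium. Laboratory TLS needs at least 2 within 24 hours. An arrhythmia with potassium of 6.0 mmol/L or more as the only abnormality has 1 of 4, and 1 < 2, so laboratory TLS is not met and clinical TLS is therefore not met. The event still fits the Table 33 row. If it is Grade 3 or higher and considered related, it also meets the stop rule.

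6. **Cases side by side** (arrhythmia or heart failure with the cause named in the footnotes):

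| Event | Table 33 | 6.6.5 / 11.4.7.2 | Result |
|---|---|---|---|
| Grade 2 | Restart one dose lower | Withhold if clinically significant; restart possible | No direct clash |
| Grade 3 or higher, not considered related | Restart one dose lower | Stop rule not triggered | No clash with the stop rule |
| Grade 3 or higher, related, recorded as a cardiac AE | Restart one dose lower | Permanent stop | Incompatible |
| Grade 3 or higher, related, recorded only as clinical TLS | Restart one dose lower | Not stated whether the stop rule applies | Silent |

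The last row is a real possibility. Appendix F 1.4 has TLS reported as laboratory or clinical TLS, and Section 8.3.4 prefers a diagnosis to a list of signs.

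7. **Which rule prevails?** Section 2.2 identifies the dose-modification guidelines as Section 6.6 and treats Appendix F as additional guidance. Section 6.6 sends cardiac AEs to 6.6.5. Section 6.6.3, which sends TLS to Appendix F, heads its Table 7 with an exception sending cardiac changes to 6.6.5. The ECG sections of both modules (11.6.2.6 and 12.6.2.6) also point to 6.6.5. Together these favour 6.6.5, but none is an express precedence clause.

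**The case against.** The strongest reply is that the protocol, read as a whole, already settles the matter. The routing in step 7 all leads to 6.6.5, and the stop rule is unqualified and stated twice. Table 33 can then be read as setting the restart dose only for patients still eligible to restart. An arrhythmia from isolated hyperkalaemia is not clinical TLS, so it belongs more naturally under 6.6.5 than in a table about TLS. Appendix F is also framed as recommendations.

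Most of this stands. It makes 6.6.5 the better-supported rule and keeps the severity low. It does not remove the defect: the harmonised reading has to be assembled from several sections, while the row itself gives a restart instruction with no exception.

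Two stronger readings are tempting. One is that the protocol compels a restart after a severe cardiac event. It does not: Section 7.1 lets the Investigator or the sponsor end treatment for any AE that contraindicates further dosing. The other is that every cardiac manifestation of TLS falls under contradictory rules. The documents do not support that either. Grade 2 and unrelated events do not clash with the stop rule, and for an event recorded only as clinical TLS the protocol is silent, not contradictory.

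**Conclusion.** Wrong as written, for a narrow overlap, at low severity. The conflict is confined to arrhythmia attributed to hyperkalaemia or hypocalcaemia, or heart failure attributed to hypocalcaemia, that is CTCAE Grade 3 or higher, considered related, and recorded as a cardiac AE.

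No probability can be attached to this. Few events are expected: the Table 31 footnote places enrolled patients at intermediate or low TLS risk, prophylaxis is required for all, and the Amendment 2 rationale reports no tumour-lysis SAEs in the 300 mg cohort (denominator not given). The SAP records that the study was terminated on 28 July 2023, which limits the practical urgency but not what the protocol says.

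The conclusion rests on reading the restart sentence in 6.6.5 as applying to withheld treatment and not to a permanent stop, and the TLS exception in 11.4.7.2 as confined to DLT assessment. The wording of both supports this.

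**What to change.** Add to the restart bullet of the Table 33 clinical-signs row: *unless the event is a cardiac AE meeting the permanent-discontinuation rule in Section 6.6.5 (related, CTCAE Grade ≥ 3), in which case Section 6.6.5 applies*. Add a matching cross-reference to Table 33 in Section 6.6.5.

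The clause should go no further. Extending the stop to events recorded only as clinical TLS would be a decision about re-challenge after a reversible electrolyte disturbance. The sponsor should make that decision and state it either way.

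The cost is one clause and one cross-reference, with no change to design, data collection or analysis. It may need handling as a protocol amendment: the Amendment 1 log classed the addition of the stop rule to 6.6.5 as substantial, although this edit adds no new rule. The clinical downside is that a patient with a reversible, electrolyte-driven, related Grade 3 or higher cardiac AE could not be re-challenged, but 6.6.5 already implies that.
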